3.1 Inclusion Criteria

Create a numbered list of the inclusion criteria that define who will be included in your final study sample (e.g., age, gender, condition, etc.)

1. Enrolled in and receiving the Nurse-Family Partnership program through the Geisinger Clinic or UPMC Home Health Care of Central PA
2. Age \geq 18 years old
3. Nulliparous pregnant woman
4. Women with a singleton viable pregnancy confirmed by NFP home visitors
5. English speaking
6. Access to reliable internet service required for data collection
7. Willingness to download and access an app on personal smartphone
8. A minimum of 5 women with use of nicotine containing products (cigarette, cigar, hookah, chewing tobacco, e-cigarette, patch) within the past 3 months

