Nicotine and Tobacco Cessation. Nicotine use, and particularly cigarette smoking is a key modifiable risk factor for CVH, in addition to numerous other maternal-child health indicators. During the pilot, we will aim to recruit at least 5 women with nicotine use in the past 3 months (cigarette, cigar, hookah, chewing tobacco, e-cigarettes, patch) into the study to pilot enhanced intervention to reduce nicotine use (and particularly cigarette smoking). Cigarette and e-cigarette use will be the most common sources of nicotine exposure, and cigarette smoking likely the most harmful. Carbon monoxide screening will be used throughout on all patients to document new exposure or recidivism, which would trigger enrollment into an enhanced intervention. We will use the Micro+™ baby Smokerlyzer® from Covita. This monitor can be used during pregnancy and postpartum. It measures three relevant feedback parameters to the patient: PPM – CO in the lungs, %COHb – CO in the blood and %FetalCOHb – fetus CO level. Baseline assessment will record ever use of any tobacco/nicotine product and from that point and at subsequent visits will focus on assessment of the average frequency of use per day over the previous 7 days. Non-smoking will be reinforced, and smokers will be provided with evidence-based education and motivational interviewing counseling based on the existing NFP protocols. In addition, as soon as women who have used a nicotine product in the previous 3 months agree, they will be assisted to call and enroll with the national smoking cessation Quitline where they will receive pro-active callback counseling, written materials, and other intervention modalities (e.g. texting and online support). These interventions will be repeated as required throughout the trial using a chronic care model rather than a single intervention model.¹²⁴ Nicotine replacement and/or medication may be provided by the Quitline according to their standard protocols for pregnant women, requiring written approval from the woman's provider, prescribed in order to achieve smoking cessation or reduction. Compliance will be monitored with carbon monoxide monitoring. We have developed a protocol and script for delivering this intervention to achieve smoking cessation (see uploaded intervention documents).

We next include a summary of the study visit table with study specific parameters on mothers only for this pilot (NOTE as per above NFP visits will be more frequent).

Table 1. Study Visit Table

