CONSTRUCT	MEASURE	Prenatal and/or Postpartum		
		Study entry (V1)	+ 1 month (V2)	+2 months (V3)
Smoking status	National Adult Smoking Survey questions	S	S	S
Home Blood Pressure Monitoring (HBPM)	Systolic/diastolic blood pressure three times a week; nurse review results at each visit and provide referrals for high readings	C / N	C / N	C / N
Carbon Monoxide (CO) Monitoring	CO monitoring will take place to monitor for smoke exposure, faulty ventilation, etc.	N	N	N
Physical Activity	Sedentary time, steps, intensity, hours/week monitored by actigraphy device	C	C	C
Demographic/baseline characteristics	Developed for ENRICH	S		S
Satisfaction	Developed for ENRICH			S

S=survey; C= client self-monitoring; N= nurse administered

MATERNAL MODIFIED AMERICAN HEART ASSOCIATION HEALTH INDICATORS

Smoking. Maternal smoking status will be assessed at baseline using items from the National Adult Smoking Survey including: “Have you ever smoked a cigarette, even one or two puffs?”; “About how many cigarettes have you smoked in your entire life?”; “During the past 30 days, on how many days did you smoke cigarettes?”; “When was the last time you smoked a cigarette, even one or two puffs?”; and “During the past 30 days, on the days you smoked, about how many cigarettes did you smoke per day?” A script is provided for the NFP nurse to administer this intervention. This will be repeated at the designated time points in Table 1 among known smokers only.

DIGITAL DEVICE MONITORING

Our plan will be to use digital devices that can be accessed through apps on participant smart phones. The participants will have immediate access to the data from the Fitbit and Fitbit Scale, through Bluetooth links to their smartphone or computer. Research data will not be collected from these devices (i.e., the research team will not have access to data from the Fitbit or Fitbit Scale). However, NFP home visiting nurse will answer any questions related to physical activity and weight as standard care. The research team will ask participants to document readings from the blood pressure monitor on a study tracking log. This log will be reviewed by the NFP visiting nurse at each home visit and referral provided for high readings as appropriate (details below).

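### Exhaled CO is the named check of compliance and relapse in a nicotine-reduction intervention, but it reads only recent combusted smoking; e-cigarette and chewing-tobacco use needs self-report assigned to that role.

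*Combined protocol and SAP*

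**What the plan says.** The Nicotine and Tobacco Cessation paragraph of section 7.2 describes an enhanced intervention whose aim is to reduce nicotine use, cigarette smoking above all. The products counted are "cigarette, cigar, hookah, chewing tobacco, e-cigarettes, patch", the same list as in section 3.1. On the expected mix it says "Cigarette and e-cigarette use will be the most common sources of nicotine exposure, and cigarette smoking likely the most harmful".

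Two tasks are given to CO. On relapse: "Carbon monoxide screening will be used throughout on all patients to document new exposure or recidivism, which would trigger enrollment into an enhanced intervention". On adherence: "Compliance will be monitored with carbon monoxide monitoring". The monitor returns "PPM – CO in the lungs, %COHb – CO in the blood and %FetalCOHb – fetus CO level" and nothing else.

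Table 1 gives the CO measurement a further purpose: "CO monitoring will take place to monitor for smoke exposure, faulty ventilation, etc".

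Self-report is also collected. Section 7.2 records lifetime use of any product at baseline and mean daily use over the past week at later visits. Sections 7.2.1 to 7.2.3 offer the cessation programme or handout according to nicotine use in the past three months. The smoking survey items listed after Table 1 ask about cigarettes only, and their repeat is restricted to women already known to smoke.

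**The concern.** The behaviour to be changed is nicotine use; the instrument named to check the change measures carbon monoxide. The two agree for products that are burned and part company for those that are not. Because e-cigarettes are expected to be common, the gap is not a rare exception.

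What is at stake is the second secondary endpoint in section 1.3, the uptake and utility of the enhanced cessation intervention. If adherence or freedom from relapse is described from CO readings, it can look better than it was. Delivery is affected too: section 7.2 repeats the intervention as needed under a chronic care model, and a relapse that CO cannot show would not prompt a repeat through that route. Section 11.2 says that the pilot is meant to inform a large multi-site trial, so a measurement rule that is loose here may be carried forward.

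**Working it through.** The plan states no CO cut-off, sensitivity, specificity or compliance rate, so there is no figure to reproduce. The check is mainly a comparison of passages.

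**Step 1: what CO can show for each product.** The premise is one of measurement, not a statement in the documents: CO is produced by burning.

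| Product in 7.2 | Burned? | Can CO separate continued use from stopping? |
|---|---|---|
| Cigarette, cigar, hookah | Yes | Yes, for recent smoking |
| E-cigarette, chewing tobacco | No | No |

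A smoker who moves to e-cigarettes shifts from the first row to the second. Her CO falls while her nicotine use goes on. The patch is left out of the table for the reason given under the objection.

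**Step 2: whether another measure is assigned to the second row.**
- The 7-day use question in 7.2 could do the job. It does not appear in Table 1, and no sentence makes it the measure of compliance or recidivism.
- The survey row in Table 1 uses items that ask about cigarettes, and the repeat leaves out women not known to smoke.
- The reported-use conditions at Visits 2 and 3 decide who receives a handout, not who has complied or relapsed.
- No passage says what happens when self-report and CO disagree.

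So the information is partly collected, but the role is given to CO.

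**Step 3: the trigger and Table 1 side by side.** Section 7.2 lets a CO-documented new exposure start the enhanced intervention. Table 1 says that the same reading looks for faulty ventilation. Neither passage says how a raised reading from a household source is told apart from one due to tobacco smoke.

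**Step 4: an illustration of size.** From 7.2, the minimum number of nicotine users is n = 5. Assumed, because the documents give no percentages: a share f of these women use only non-combusted products, independently of one another.

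- Expected number unreadable by CO = n × f: 5 × 0.2 = 1; 5 × 0.4 = 2; 5 × 0.6 = 3.
- Chance of at least one = 1 − (1 − f)^5: 1 − 0.8^5 = 0.672; 1 − 0.6^5 = 0.922; 1 − 0.4^5 = 0.990.
- In a group of five, one woman read wrongly moves a reported proportion by 1/5 = 20 percentage points.

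No similar figure is offered for raised readings from household sources, because the documents give nothing to base it on.

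**The case against.** The strongest reply is that CO is not the only information on use. The 7-day question and the reported-use conditions run alongside it, so a design that classifies women by CO alone is not what the protocol describes. This stands, and it limits the claim: women can be misread where CO is relied on. A reader might infer that women will be misclassified in both directions; the documents do not support that.

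Second, the compliance sentence sits between one on nicotine replacement or medication and one on a script for smoking cessation. Read there, compliance may simply mean not smoking, which CO does address. That is a fair reading, but the paragraph as a whole sets nicotine reduction as the aim and never limits CO to smoked products. The same context removes the patch as an example: nicotine replacement may be part of the treatment, so a CO reading that ignores it is no error when judging smoking.

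Third, the endpoint in 1.3 concerns women who smoke or have environmental smoke exposure. Second-hand smoke is therefore in scope, and only a non-tobacco source is out of place. A reader might infer that a non-user with faulty ventilation would enter the cessation pathway and be counted in its uptake. That does not follow. Quitline enrolment, the Visit 1 programme and the later handouts all depend on nicotine use, and no uptake denominator is defined. What remains is that the general trigger sentence and Table 1 do not fit together as written.

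Fourth, section 8.3 is descriptive and builds no cessation outcome on CO. This too stands, and it keeps the point modest. It is also tempting to work out how few days the CO readings cover. That would need an elimination time that the documents do not give and a fixed number of readings, whereas Table 1 shows three and 7.2 says screening is used throughout. It would also ignore the 7-day recall.

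**Conclusion.** The concern holds in limited form. As written, the named check of compliance and recidivism cannot detect continued or resumed use of e-cigarettes or chewing tobacco, although both are within the stated target and e-cigarettes are expected to be common. Self-report that could fill the gap is planned but has not been given that role.

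The number of women affected is not derivable from the plan. Under the assumed 20-60% share, 1 to 3 of five nicotine users would be expected to be unreadable by CO. The conclusion rests on the premise that CO reflects combustion and on the plain wording of 7.2. It touches a secondary endpoint and the delivery of the intervention, not the primary endpoints in 1.2. It should be corrected, since the remedy is already largely in the protocol.

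**What to change.** In section 7.2:

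1. State that CO verifies recent combusted smoking only, and that a low reading does not rule out relapse.
2. For e-cigarette and chewing-tobacco users, make the 7-day use question, asked for any product, the measure of compliance and recidivism. List it in Table 1 so that it is not confined to known smokers.
3. Report users of combusted and non-combusted products separately in the descriptive results under 8.3.
4. Record the apparent source beside each raised CO reading, and report non-tobacco sources separately.
5. Reconcile the sentence by which a CO-documented exposure triggers the enhanced intervention with the faulty-ventilation purpose in Table 1. Which reading should start the intervention is for the sponsor to decide.

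The cost is a few lines of text and one field beside each reading, with no new test or staff. The downside is that compliance for non-smoked products then rests on self-report, which the report should say openly.

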1.3 Secondary Study Endpoints

State the secondary endpoints to be measured in the study.

- Successful uptake and demonstrable utility of actigraphy and intermittent home-based blood pressure monitoring (HBPM) during and after pregnancy.
- Successful uptake and demonstrable utility of an enhanced smoking cessation intervention among women who smoke or have environmental smoke exposure.

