7.2.2 Visit 2 or Day 2 or Post-test, etc. (If applicable)

Provide a description of what procedures will be performed on visit 2 or day 2 or post-test in order of how these will be done. If your study involves more than two sessions or visits replicate this section for each additional session or visit (e.g., 7.2.3, 7.2.4, etc.).

Study Visit 2 (V2) as summarized in Table 1 will take place about 1 to 2 months after the participants first study visit. At this visit, participants will receive “Physical Activity During Pregnancy” handouts that includes information on safely adding physical activity into their daily life from their visiting nurse. The NFP visiting nurse will also answer any questions participants have about physical activity and weight monitoring. The NFP visiting nurse will also review results and answer any questions about the results from participant home blood pressure monitoring. In addition, participants who report using nicotine products in the past 3 months, will be provided with a handout on the benefits of and tips for quitting smoking during or after pregnancy.

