8.3 Statistical methods

Describe the statistical methods (or non-statistical methods of analysis) that will be employed.

Descriptive statistics for surveys as well as feasibility (e.g., recruitment and retention, fidelity, data collection methods) and acceptability (e.g., satisfaction) will be calculated.

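### The repeat smoking survey is limited to undefined known smokers, although Table 1 schedules it without a limit and CO screening looks for new exposure in every woman

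*Combined protocol and SAP*

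**What the plan says.** Four parts of section 7.2 bear on who is asked about smoking after baseline.

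- **Table 1, smoking status row.** The measure is "National Adult Smoking Survey questions", marked as a survey at V1, V2 and V3. No footnote restricts it.
- **Smoking paragraph below Table 1.** After listing five items for baseline, it says: "This will be repeated at the designated time points in Table 1 among known smokers only". It does not say what makes a woman a known smoker.
- **Nicotine and Tobacco Cessation.** Assessment "at subsequent visits will focus on assessment of the average frequency of use per day over the previous 7 days", with no restriction to smokers. On CO: "Carbon monoxide screening will be used throughout on all patients to document new exposure or recidivism, which would trigger enrollment into an enhanced intervention".
- **Table 1, CO row.** "CO monitoring will take place to monitor for smoke exposure, faulty ventilation, etc". The nurse takes the measurement at V1, V2 and V3.

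Section 7.2.2 adds that at V2 "participants who report using nicotine products in the past 3 months, will be provided with a handout", and section 7.2.3 says the same for V3. The related secondary endpoint in section 1.3 is "Successful uptake and demonstrable utility of an enhanced smoking cessation intervention among women who smoke or have environmental smoke exposure". Section 8.3 plans "Descriptive statistics for surveys as well as feasibility" and acceptability, and names no specific smoking analysis.

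**The concern.** A nurse who works from Table 1 surveys every woman at V2 and V3. A nurse who works from the paragraph below it surveys only those she regards as smokers. Two agencies deliver the programme, so practice could differ between them.

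The restriction also works against the purpose of the CO screening. That screening covers everyone because a woman may start smoking, relapse or become exposed during follow-up. Starting and relapse arise among women not currently classed as smokers, and those are the women whom the narrower rule drops from the repeat survey. A CO reading alone does not say where the CO came from: Table 1 itself gives smoke exposure and faulty ventilation as possible sources. The woman's own answer about recent cigarettes is the natural companion to the reading.

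At stake is the descriptive summary of smoking at V2 and V3. Under the narrower rule it describes a subgroup fixed by an undefined label, and it cannot itself record new smoking in anyone else.

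**Working it through.** The plan gives no figure to reproduce: section 8.2 states that no formal sample size calculation was made. The check is a comparison of texts followed by a head count.

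**Comparison**

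| Place in 7.2 | What is done at V2 and V3 | In whom |
|---|---|---|
| Table 1, smoking row | Named smoking survey | No limit stated |
| Smoking paragraph | Named smoking survey | Known smokers (undefined) |
| Nicotine and Tobacco Cessation | Frequency of use, previous 7 days; no survey named | No limit stated |
| Nicotine and Tobacco Cessation; Table 1, CO row | CO measurement | All women |

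The first two rows conflict as written. The third does not name the survey but is also unrestricted.

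**Inputs**

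- Planned enrolment: 20 women (section 8.1).
- Visits with a survey and a CO measurement: 3, of which 2 are follow-up (Table 1).
- Recent nicotine users: at least 5 sought (sections 3.1 and 7.2). They may be users of e-cigarettes, chewing tobacco or patches as well as cigarettes.
- Number of known smokers, k: not given. I use 5 and 10 as illustrations, and 0 as the extreme in which none of the nicotine users counts as a smoker.
- Assumed: full retention, and one CO reading per woman at each Table 1 visit.

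**Formulas**

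- Surveys scheduled by Table 1: 20 x 3 = 60.
- Surveys done under the narrower rule: 20 at V1 plus 2k at V2 and V3, that is 20 + 2k.
- Follow-up CO readings: 20 x 2 = 40.
- Follow-up CO readings with no survey beside them: 2 x (20 - k).

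| k | Surveys done, of 60 | Women surveyed at V2 and V3, of 20 | Follow-up CO readings without the survey, of 40 |
|---|---|---|---|
| 0 | 20 | 0 | 40 (100%) |
| 5 | 30 | 5 | 30 (75%) |
| 10 | 40 | 10 | 20 (50%) |

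The k = 0 row is needed because the enrolment target counts nicotine users, while the survey rule counts smokers. A woman who uses only a patch or an e-cigarette meets the first and may not meet the second, so k = 5 is not a lower bound.

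These counts are of one named survey that is absent. They are not counts of readings without any smoking information, nor of raised CO readings, whose frequency the documents do not give.

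**The case against.** The best defence is that nothing conflicts. Section 7.2 introduces Table 1 as a summary, and the paragraph below it cites the table and then says who is asked. Text that qualifies a summary table is normal, and two of the five listed items (ever smoked, lifetime cigarettes) gain little from repetition. Screening everyone by CO and then surveying those who smoke is also a coherent two-step design, because a raised reading or a self-report could make a woman known. Part of this stands: the two background items need not be repeated. But a qualification works only if its key term is defined, and no text says that a raised reading brings a woman into the repeat survey.

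A second defence is that the sentence refers to the scripted intervention mentioned just before it, which would properly be limited to smokers. The survey is the better reading. The sentence points to time points in Table 1, and the table has a row for the smoking survey and none for the intervention. If the intervention was meant, the sentence still needs rewording.

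A third defence is that later smoking is already covered, and this limits the point. The 7-day assessment is unrestricted, and the V2 and V3 handouts depend on reported nicotine use, so some question is probably put to every woman. A reader might infer that women not known to smoke yield no smoking information after baseline. The documents do not support that.

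**Conclusion.** The inconsistency is real and the point is minor. As written, the repeat survey is limited to an undefined group, while the schedule and the neighbouring text set no such limit. Under that rule 20 to 30 of the 40 follow-up CO readings would lack the survey for k from 10 down to 5, and up to 40 if k = 0. This rests on full retention, one CO reading per Table 1 visit and assumed values of k. The consequence is small because the study is a 20-woman, single-arm pilot with descriptive statistics, and no primary endpoint in section 1.2 names smoking status or CO.

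Three stronger readings are tempting and should not be drawn.

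- **That second-hand smoke is never asked about.** The five listed items concern the woman's own cigarettes, and the section 1.3 endpoint reaches further. But the list is introduced as partial, the household questionnaire is not shown, and the protocol template tells authors to leave survey questions out. The CO row also covers smoke exposure.
- **That nothing is done about a household CO source.** No visible text gives a specific step, but the cessation script is uploaded separately and is not shown, and section 17.5 gives a general route for concerns about the intervention material.
- **That a non-smoker with a raised reading would be sent to cessation in error.** Although CO findings are said to trigger the enhanced intervention, the cessation steps that are spelled out depend on nicotine use or on the woman's agreement.

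**What to change.** In the Smoking paragraph of section 7.2, delete the last four words of the sentence on repeats, so that all women answer at V2 and V3 as Table 1 shows. State that the repeat consists of the three recent-use items (days smoked in the past 30, time of last cigarette, cigarettes per day on smoking days). The ever-smoked and lifetime items can stay at baseline only.

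The cost is 2 x (20 - k) extra short repeats: 30 at k = 5, 20 at k = 10 and at most 40. All fall at visits already scheduled, so no visit or test is added. A footnote to Table 1 that defines known smokers and keeps the limit would remove the contradiction at no burden to participants, but it would leave the CO readings of the other women without the survey.

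Two optional checks against the uploaded materials: whether the survey asks about other people's smoke in the home, and whether the script tells the nurse what to do about a raised CO reading that smoking does not explain. If either is there, a reference in section 7.2 is enough. If not, the sponsor can decide whether to add it. A referral step would need a stated CO threshold and an estimate of the referrals it would generate, and the documents give no basis for either.
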